#### Exclusion Criteria – IBS Group:

History of anti-anxiety/depressant medication (SSRIs/SNRIs, Chinese patent medicines, etc.)

within the past month

History of antibiotics or probiotics use within the past month

Inflammatory bowel disease (IBD), intestinal obstruction, other gastrointestinal diseases, or gastrointestinal surgery

Current or past psychiatric or neurological disorders (e.g., psychosis, brain tumors, consciousness disorders)

Severe hepatic/renal insufficiency, cardiovascular/cerebrovascular disease, or malignancy

Contraindications to 7.0T MRI:

Ferromagnetic implants (cardiac pacemaker, defibrillator, neurostimulator, aneurysm clip, cochlear implant, or any metallic foreign body)

Non-ferromagnetic implants (e.g., titanium alloy, orthopedic implants), intrauterine devices, non-removable dentures (including implants)

Metal foreign bodies in eyes or body (metal fragments, shrapnel, metal shavings), history of welding work or metallic foreign body injury

Tattoos or permanent makeup (eyebrows, lips) within the last month

Claustrophobia

Fever

Inclusion Criteria – Healthy Control (HC) Group:

Right-handed, aged 18–60 years, education  $\geq 6$  years

All physiological indices within normal range, no disease manifestations

No family history of psychiatric or neurological disorders

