## 5. SAMPLE SIZE JUSTIFICATION

Based on prior literature and preliminary data, sample size is calculated using the formula for comparing means between two independent samples:

$$n = [2 \times (Z\alpha/2 + Z\beta)^2 \times \sigma^2] / \delta^2$$

Parameters:

Significance level:  $\alpha = 0.05$  (two-sided)

Power:  $1 - \beta = 80\%$

Effect size:  $\delta = 0.5$

Standard deviation:  $\sigma = 1.0$

Calculation: Minimum 64 subjects per group. Considering a 20% dropout rate, the final target is 100 IBS patients and 100 healthy controls.

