## 6. STUDY PROCEDURES AND ASSESSMENTS

### 6.1 Case Report Form (CRF) Modules

#### Module 1: Demographics

Age, sex, education, height, weight, BMI, lifestyle (smoking/alcohol history)

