#### Module 5: Biospecimen

Fecal metagenomic sequencing; serum and fecal metabolomics

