### 7.2 Statistical Analysis

Group comparisons: Independent t-test (normal distribution) or Mann-Whitney U test (non-normal)

Correlation analysis: Pearson or Spearman correlation coefficients

Multi-omics integration: Sparse Canonical Correlation Analysis (sCCA), Principal Component Analysis (PCA)

Machine learning: Random Forest for key biomarker selection; ROC curve for diagnostic efficacy evaluation

Covariate adjustment: Age, sex, BMI, and other confounders in multivariate regression models

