## 8. BIAS CONTROL AND QUALITY MANAGEMENT

### 8.1 Bias Control

Selection bias: Strict adherence to inclusion/exclusion criteria; consecutive enrollment

Measurement bias: Double-blind psychiatric evaluation; automated imaging analysis algorithms

Confounding bias: Multivariate regression adjustment for age, sex, BMI

Reporting bias: Protocol pre-registration on ClinicalTrials.gov; results reported per STROBE guidelines

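### Controls, but not IBS patients, must pass an undefined all-indices-normal screen; if it covers blood values, it can create group differences in serum metabolites that IBS did not cause

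*Protocol*

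**What the plan says.** In the protocol, section 4.2, the healthy-control inclusion criteria require "All physiological indices within normal range, no disease manifestations". The text does not say which indices, which ranges, or when they are measured.

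The IBS group has no normal-range requirement. Its nearest criterion excludes "Severe hepatic/renal insufficiency, cardiovascular/cerebrovascular disease, or malignancy". The exclusions for recent antibiotics or probiotics and for recent anti-anxiety or antidepressant medication also stand under the IBS group only.

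Section 6.1, Module 5, collects "Fecal metagenomic sequencing; serum and fecal metabolomics", and section 6.2 schedules blood and stool sampling at baseline. Section 7.2 compares groups by t-test or Mann-Whitney test, then uses Random Forest to pick biomarkers and ROC curves to judge them. A separate line adjusts for "Age, sex, BMI, and other confounders in multivariate regression models".

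Section 8.1 names its safeguard: "Selection bias: Strict adherence to inclusion/exclusion criteria; consecutive enrollment".

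**The concern.** One group is selected on physiology and the other is not, and the two are then compared on physiology. If the screen includes blood values, the control distribution of those values, and of any metabolite correlated with them, is cut off, while the patient distribution keeps its tails. A difference between groups can then reflect the screening rule and not IBS.

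The unadjusted comparisons in section 7.2 do not remove such a difference. The safeguard in section 8.1 does not help, because strict adherence to the criteria enforces the asymmetry. Eligibility is fixed in the protocol, so this is not a detail that a later analysis plan would normally settle: no analysis brings back controls who were screened out. At stake are the case-control findings on serum metabolites and any diagnostic biomarker derived from them.

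**Working it through.** **The plan's own figure.** Inputs from section 5: two-sided alpha 0.05, power 80%, difference 0.5, SD 1.0. The formula gives 2 × (1.960 + 0.842)² × 1 / 0.5² = 62.8, so 63; the t-based solution is 63.8, so 64 per group, as stated. The target is 100 per group. The protocol gives no figure for selection bias, so the rest is a sensitivity calculation.

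**Assumptions not in the documents.** IBS has no effect. Patients follow the source population, N(0,1) on the screened index. Controls follow the same distribution cut at the limit. A share p of the source population exceeds a one-sided upper limit. A metabolite has correlation rho with the index.

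**Formulas.** With c = z(1−p):
- control mean of the index: m = −φ(c)/(1−p), with truncated variance v;
- metabolite shift: rho × m; control variance of the metabolite: 1 − rho² × (1−v);
- standard error of the difference: √[(1 + control variance)/100];
- false-positive rate: Φ(|shift|/SE − 1.96) + Φ(−|shift|/SE − 1.96).

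**Worked case, p = 20%.** For the index itself, m = −0.350 and control SD is 0.764, so SE = √[(1 + 0.584)/100] = 0.126, the ratio is 2.78, and the rate is 79%. For rho = 0.5, the shift is −0.175, the control variance is 1 − 0.25 × 0.416 = 0.896, SE = 0.138, the ratio is 1.27, and the rate is 25%.

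| Share over a one-sided limit | Shift of index (SD) | Control SD | Rate, index itself | Rate, rho 0.5 | Rate, rho 0.3 |
|---|---|---|---|---|---|
| 5% | −0.109 | 0.900 | 13% | 6.7% | 5.6% |
| 10% | −0.195 | 0.844 | 32% | 10.8% | 7.0% |
| 20% | −0.350 | 0.764 | 79% | 24.6% | 11.6% |
| 30% | −0.497 | 0.702 | 98% | 44.2% | 18.7% |

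**Symmetric range.** If controls must lie in the central 95%, 90% or 80%, the mean shift is 0 and the false-positive rate stays near 5%. Only the control SD falls, to 0.87, 0.79 and 0.66.

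**Why the spread still matters for a classifier.** Out-of-range values then occur only among patients. With one 95% range, 5% of unaffected patients and no controls are flagged: AUC = (1 + 0.05)/2 = 0.525. With 20 independent ranges, 1 − 0.95^20 = 64% of patients are flagged: AUC = (1 + 0.64)/2 = 0.82. This needs the screened analytes to be among the classifier's inputs and a panel of that size, neither of which the protocol states.

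**Adjustment.** In simulations (4,000 runs per setting; 10%, 30% or 50% excluded; rho 0.3, 0.5 or 0.7), adding the screened index as a linear covariate brought the false-positive rate back to between 4.6% and 5.5%.

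**The case against.** The strongest reply is that the protocol names no blood value or body measure as a screening index. The CRF modules in section 6.1 list no clinical chemistry, the baseline blood draw is described as sample collection, and the CRF and SOPs are appendices that are not shown. Requiring healthy controls to be healthy is also common, and buys a clean reference group. This stands as a limit on what can be claimed: a metabolite bias is conditional on what the indices turn out to be. It does not remove the asymmetry, and a rule that covers all indices without listing them cannot be applied reproducibly.

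Four stronger readings are tempting, and the documents do not support them:
- **That differences will appear.** They can appear. A symmetric range shifts no mean, and a rare abnormality or a weak correlation shifts it very little.
- **That the bias matches the 0.5 SD design effect.** That needs about 30% of the source population over a one-sided limit, and the outcome must be the screened index itself. If 2.5% to 5% exceed a one-sided limit, the shift is 0.06 to 0.11 SD.
- **That adjustment cannot undo it.** Section 7.2 names BMI as a covariate, so a BMI screen is handled wherever the regression models are used, and other confounders are allowed for. The problem remains in the unadjusted tests and for screened indices left out of the model.
- **That most healthy volunteers would fail.** This assumes a large laboratory panel that the protocol does not mention.

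The scope is also limited. Serum metabolomics is one data type beside stool omics and 7T MRI, and associations estimated within the IBS group do not depend on how controls were chosen.

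**Conclusion.** The point holds in a conditional form. What is certain from the text is that an undefined normal-range screen applies to controls only, that the groups are compared by unadjusted tests, and that section 8.1 relies on the same criteria as its protection against selection bias.

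The size is uncertain. Under a one-sided limit exceeded by 5% to 20% of the source population, one screened index and 100 per group, the shift is 0.11 to 0.35 SD on that index, with false-positive rates of 13% to 79%; at a correlation of 0.5 the rates are 7% to 25%. If only vital signs are meant, the effect on metabolites is smaller. Confidence is high in the asymmetry and low in any single magnitude. A short amendment is justified because the correction is cheap and the selection cannot be reversed afterwards.

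**What to change.** **Preferred.** Define control health as absence of disease, and apply the IBS group's exclusion list to controls as well. That includes the items now stated for the IBS group only, such as antibiotics or probiotics and anti-anxiety or antidepressant medication in the past month, which bear directly on the microbiome and metabolome.

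**If a normal-range screen is kept.** List the indices and their limits, then either apply the same screen to both groups or record the indices in both groups and include them as covariates in the group comparisons. Adjustment does not help for an analyte that is both a screening index and the outcome, so such analytes should not be used to screen one group alone.

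**Controls already enrolled.** Keep them, record which version of the rule admitted each one, and add a sensitivity analysis by rule version.

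**Cost.** The preferred option is a short protocol amendment with no new test, and its downside is a slightly more heterogeneous control group. Screening patients too could require tests that the protocol does not describe, so it is the dearer option.

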## 5. SAMPLE SIZE JUSTIFICATION

Based on prior literature and preliminary data, sample size is calculated using the formula for comparing means between two independent samples:

$$n = [2 \times (Z\alpha/2 + Z\beta)^2 \times \sigma^2] / \delta^2$$

Parameters:

Significance level:  $\alpha = 0.05$  (two-sided)

Power:  $1 - \beta = 80\%$

Effect size:  $\delta = 0.5$

Standard deviation:  $\sigma = 1.0$

Calculation: Minimum 64 subjects per group. Considering a 20% dropout rate, the final target is 100 IBS patients and 100 healthy controls.

## 6. STUDY PROCEDURES AND ASSESSMENTS

### 6.1 Case Report Form (CRF) Modules

#### Module 1: Demographics

Age, sex, education, height, weight, BMI, lifestyle (smoking/alcohol history)

#### Module 2: Clinical Assessment

Rome IV criteria score, abdominal pain frequency/intensity, Bristol Stool Scale

#### Module 3: Psychological Evaluation

Auditory Verbal Learning Test, Color Test, Montreal Cognitive Assessment (MoCA), Memory Span Test, Beck Anxiety Inventory (BAI), Beck Depression Inventory (BDI), Pittsburgh Sleep Quality Index (PSQI)

#### Module 4: Imaging Data

7T MRI: structural, functional, and metabolic imaging

#### Module 5: Biospecimen

Fecal metagenomic sequencing; serum and fecal metabolomics

#### Module 6: Follow-up

Symptom remission time, medication use, adverse events

### 6.2 Follow-up Schedule

#### Baseline (Enrollment):

Complete clinical assessment, psychological scales, MRI scan, fecal/blood sample collection

#### 3-Month Follow-up (IBS Group Only):

Repeat anxiety/depression scales

Repeat fecal/blood sample collection

Assess symptom relief (abdominal pain frequency, stool characteristics)

#### 6-Month Follow-up (Optional):

Long-term efficacy tracking

Repeat imaging data collection (selected patients)

#### Follow-up Workflow:

Subjects sign informed consent and enter baseline assessment

Research nurses remind follow-up appointments via telephone/outpatient visits

Complete CRF at each follow-up and upload to Electronic Data Capture (EDC) system

Data manager reviews and locks data

## 7. DATA MANAGEMENT AND STATISTICAL ANALYSIS

### 7.1 Data Management

Platform: REDCap electronic data capture system

Entry: Double independent data entry with verification

Cleaning: Exclude variables with >20% missing values; use multiple imputation for missing data

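### The 20% missing-variable deletion rule has no denominator, visit scope or exemption, and conflicts with the follow-up schedule and the planned dropout

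*Protocol*

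**What the plan says.** Protocol section 7.1 (Data Management) gives the whole rule in one line: "Cleaning: Exclude variables with >20% missing values; use multiple imputation for missing data". It makes no distinction between a value that was never scheduled, one lost to dropout and one below a detection limit.

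Three other places bear on it:

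- Section 6.2, first follow-up visit, headed "3-Month Follow-up (IBS Group Only": controls have no such visit. The visit includes "Repeat anxiety/depression scales", repeat stool and blood samples, and symptom relief.
- Section 6.2, second follow-up visit, headed "6-Month Follow-up (Optional": its imaging item reads "Repeat imaging data collection (selected patients". The number to be selected is not given.
- Section 5 (Sample Size Justification): "Calculation: Minimum 64 subjects per group", then "Considering a 20% dropout rate", and "the final target is 100 IBS patients and 100 healthy controls".

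**The concern.** The protocol fixes a numeric deletion rule, and a data manager could apply it at the cleaning stage. The schedule makes some variables incomplete by design. If design gaps count as missing, the rule removes the only longitudinal data the study collects: repeat anxiety and depression scores, repeat samples, symptom relief and repeat imaging. If they do not count, the threshold still equals the only attrition figure the protocol gives, so whether the 3-month data survive depends on a handful of patients. Either way the choice of denominator is left open until the missingness has been seen. That weakens the protection against selective reporting that section 8.1 seeks through pre-registration.

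A second, conditional worry concerns the omics features. If non-detects are stored as missing, a threshold pooled over both groups can remove a feature precisely because one group lacks it.

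**Working it through.** **Inputs.** 100 IBS patients and 100 controls, and 20% dropout (section 5). IBS-only 3-month visit, and 6-month imaging in selected patients (section 6.2). Exclusion when missingness exceeds 20% (section 7.1). Assumptions: IBS patients drop out independently with a common probability d; the patients selected for repeat imaging are IBS patients; the number re-imaged, s, is unknown and is varied.

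**1. The plan's own figure.** The section 5 formula with δ = 0.5, σ = 1.0, two-sided α = 0.05 and 80% power gives 2 × (1.960 + 0.842)² / 0.25 = 62.79, so 63. The t-test version gives 63.77, so 64. The stated minimum of 64 is reproduced. Allowing for 20% dropout gives 64 / 0.80 = 80. The target of 100 is more generous and is not at issue here.

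**2. Three-month variables.** Over all subjects, the missing fraction is (100 + 100d) / 200. Over IBS patients only, it is d on average, and deletion needs at least 21 of 100 missing. That probability is P(X ≥ 21) with X ~ Binomial(100, d).

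| Dropout d | Missing, all 200 | Missing, IBS only | P(more than 20 of 100 missing) |
|---|---|---|---|
| 0 | 50% | 0% | 0 |
| 10% | 55% | 10% | 0.08% |
| 20% | 60% | 20% | 44% |
| 25% | 62.5% | 25% | 85% |

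On the first denominator the variable is deleted in every row. On the second, exactly 20% is not above 20%, so it is kept, but with no margin.

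**3. Six-month imaging.** The missing fraction is 1 − s/200 over all subjects and 1 − s/100 over IBS patients.

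| Re-imaged s | Missing, all 200 | Missing, IBS only |
|---|---|---|
| 20 | 90% | 80% |
| 50 | 75% | 50% |
| 79 | 60.5% | 21% |
| 80 | 60% | 20% |

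Over all subjects it is always deleted, since even s = 100 leaves 50% missing. Over IBS patients it is kept only if s ≥ 80. If only the selected patients are counted, the design gap disappears.

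**4. Omics features, only if non-detects count as missing.** With equal groups, pooled missingness is 1 − (p_IBS + p_HC)/2, where p is the fraction in which the feature is detected. For p_IBS = 1 this is (1 − p_HC)/2, which exceeds 0.20 when p_HC < 0.60.

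| Detected in IBS / HC | Pooled missing | Result |
|---|---|---|
| 100% / 0% | 50% | deleted |
| 95% / 60% | 22.5% | deleted |
| 100% / 60% | 20% | kept |
| 80% / 80% | 20% | kept |

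Under that coding a perfect presence/absence marker is removed, while a feature detected equally often in both groups stays.

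**The case against.** The best defence is that a sensible analyst would not count a control as missing at a visit the control was never due to attend, nor an unselected patient as missing a scan. On that reading the planned 20% dropout sits at the threshold and the 3-month data are kept. This stands as far as it goes: a reader might infer that the rule certainly deletes the follow-up data, but that follows only from the all-subject denominator, which section 7.1 does not state.

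The 20% in section 5 also inflates both groups, although only IBS patients have a 3-month visit. It is therefore not a stated 3-month attrition rate, and the 44% is conditional on taking it as one. The range from 0.08% to 85% shows how much depends on that.

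The main purpose is not at risk either. The objectives in section 3 do not mention change over time, section 5 sizes a two-group comparison, and section 7.2 lists no longitudinal model. This too stands.

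On omics, a reader might infer that the protocol imputes non-detects as if missing at random, shrinks true group differences and discards the strongest biomarkers. The protocol does not support that. It does not say non-detects are coded as missing, and it names no imputation model or missing-at-random assumption. Metagenomic absences may be recorded as zeros. Features detected in everyone but differing in level are untouched by the rule, and section 7.2 already allows a rank test. Such details may also sit in an analysis plan that is not shown.

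What the defence does not remove is the conflict between a stated, unqualified deletion rule and the protocol's own schedule.

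**Conclusion.** The point holds as a conflict within the protocol. Applied literally to the 200-subject file, the rule removes every 3-month variable (50% to 60% missing at 0 to 20% dropout) and all repeat imaging. Applied to IBS patients only, it leaves the 3-month data with a 44% chance of deletion at 20% dropout. That figure assumes independent dropout and takes the section 5 rate as the 3-month rate. Repeat imaging then needs at least 80 of 100 patients. The loss would fall on follow-up data; the baseline IBS-control comparison does not depend on these variables. The omics consequence is real only if non-detects are treated as missing, which the protocol leaves open.

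**What to change.** Amend section 7.1 as follows:

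- Count missingness for each variable only among participants scheduled for that assessment: IBS patients at 3 months, and those selected for imaging at 6 months.
- Exempt clinical, BAI/BDI, MRI and follow-up variables from deletion, and limit the 20% threshold to omics features.
- State how non-detects are coded. If they count as missing, keep a feature detected in at least 80% of either group, treat below-detection values as left-censored or lowest rank, and reserve multiple imputation for values that were not measured.

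The cost is about one paragraph of text. Slightly more omics features enter the analysis, so there is slightly more multiplicity. The by-group filter uses the case label, so it must be applied inside the training folds of the Random Forest and ROC validation; applied beforehand to the full data, it can make diagnostic performance look better than it is. Exempted variables may carry more than 20% missing values, so their missing fraction should be reported with the results.

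### Imputing once at data cleaning, ahead of all analyses, can inflate the Random Forest AUC if the model uses the classifier's label, or shrink group differences if it omits group

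*Protocol*

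**What the plan says.** Protocol section 7.1 (Data Management) puts two rules on its cleaning line. The first is "Exclude variables with >20% missing values". The second is "use multiple imputation for missing data".

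Section 7.2 (Statistical Analysis) lists the analyses. Two matter most here:

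- "Independent t-test (normal distribution) or Mann-Whitney U test (non-normal"
- "Random Forest for key biomarker selection; ROC curve for diagnostic efficacy evaluation"

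Correlations, sCCA, PCA and covariate-adjusted regression appear in the same list. Section 7.2 mentions no further missing-data method. The protocol does not name the imputation model, the label the Random Forest predicts, or any cross-validation or hold-out set.

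**The concern.** The two uses of the filled data need different imputation models.

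- **Group tests and regressions** need group in the imputation model. Without it, missing values in both groups are drawn around one common mean and the difference between groups is diluted.
- **A classifier under evaluation** needs its label kept out. Otherwise a held-out subject's filled values are drawn using the very label the classifier is asked to predict. This happens before any folds exist, so ordinary cross-validation cannot detect it.

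One imputation made at cleaning cannot meet both needs when the classifier's label is the group. At stake are the diagnostic-biomarker objective (section 3), which rests on the ROC result, and the two-group comparison on which section 5 sizes the study. An AUC inflated in this way cannot be recognised from the published figure.

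**Working it through.** **Inputs from the protocol.** Section 5: two-sided alpha 0.05, power 80%, difference 0.5, SD 1.0; "the final target is 100 IBS patients and 100 healthy controls"; 20% dropout. Section 7.1: up to 20% missing per retained variable.

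**Assumptions, not in the protocol.** Missing rates of 5%, 10% and 20%; 100 to 1,000 features; independent normal features; values missing completely at random; 5-fold cross-validation; classifier label equal to the group label.

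**1. The plan's own figure.** n = 2 × (1.96 + 0.842)² × 1.0² / 0.5² = 62.8, so 63 by the normal approximation. The t-based solution is 63.77, rounded up to 64. The stated 64 per group is reproduced.

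**2. Group omitted from the imputation model.** With a fraction m missing in each of two equal groups and no informative auxiliary variable, each group mean becomes (1 − m) × own mean + m × common mean. The expected difference is therefore (1 − m) × 0.50. Nominal power is Φ(difference × √(n/2) − 1.96), with the SD held at 1.0 and the filled data treated as complete:

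| Missing | Difference | Power, 64 per group | 80 per group | 100 per group |
|---|---|---|---|---|
| 0% | 0.500 | 80.7% | 88.5% | 94.2% |
| 5% | 0.475 | 76.6% | 85.2% | 91.9% |
| 10% | 0.450 | 72.1% | 81.2% | 88.9% |
| 20% | 0.400 | 61.9% | 71.6% | 80.7% |

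Simulated differences agree: 0.48, 0.45 and 0.39-0.40 with group omitted, against 0.49-0.50 with group included. A separate simulation at 20% missing and 100 per group (400 runs, 20 imputations, Rubin's rules) gave a difference of 0.41 and power of 78%, against 89% for a complete-case t-test.

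**3. Label included in the imputation model.** A pure-noise feature still shows a chance group difference. At 20% missing, with 80 observed per group, its standard error is √(2/80) = 0.16 SD. The imputation copies that chance difference into the missing cells of every subject, including those later held out, and the forest learns the same difference from the training folds. Each feature contributes little, but the effect accumulates over features and grows with the missing fraction.

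Random Forest, 5-fold AUC, 100 versus 100, no true signal (6 to 12 runs per row; standard error 0.009 to 0.028 in the label-included column and up to 0.030 elsewhere):

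| Features | Missing | Before split, label included | Before split, label omitted | Inside folds, label omitted |
|---|---|---|---|---|
| 100 | 5% | 0.51 | 0.50 | 0.49 |
| 100 | 10% | 0.55 | 0.50 | 0.51 |
| 100 | 20% | 0.60 | 0.49 | 0.51 |
| 500 | 10% | 0.55 | 0.49 | 0.50 |
| 500 | 20% | 0.66 | 0.52 | 0.50 |

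- Larger panels, label included: 0.56 at 5% (1,000 features), 0.58-0.59 at 10% and 0.68-0.75 at 20% (300 to 1,000 features). A repeat with 12 runs per setting gave about 0.54, 0.58-0.63 and 0.70-0.76, so the ends of these ranges are approximate.
- Choosing the top 20 features inside the folds lowers the AUC to 0.54, 0.55 and 0.64 but does not remove the excess.
- Averaging predictions over five imputations does not help: 0.61 at 20% missing with 100 features.
- With five true features of 0.5 SD among 100 and 20% missing, the AUC is 0.71 with the label included, 0.66 on complete data and 0.61 with the label-free fill inside folds.

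Imputing before the split without the label stayed near 0.50 under the null, so the fault lies in using the label.

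**The case against.** The strongest reply is that the fault is inferred. Section 7.1 does not say that one imputed set serves every analysis or that diagnosis is a predictor. Imputation models and fold-wise fitting are usual content of an analysis plan, and that plan is not shown. This stands as a limit on the wording. It does not remove the point: the protocol does fix the stage at which imputation happens, and an analysis plan that follows that order would inherit the problem.

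A reader might go further and infer that one reported result must be wrong however the imputation is built. The documents do not support that.

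- **The label is not stated.** Section 3 seeks biomarkers for IBS with psychiatric comorbidity. If the forest predicts comorbidity within IBS, the IBS/control label is constant there and leaks nothing, and group can stay in the model for the group tests. The conflict returns only if the comorbidity label, or the BAI and BDI scores behind it, enters the imputation model, as the correlations and regressions would call for.
- **No cross-validation is stated.** If none is done, its absence is the larger fault. The claim here is only that adding it would not cure the leak.
- **The effect can be small.** At 5% missing with 100 features the AUC is 0.51. With a whole panel missing at once in 5% of subjects (300 features) it is also 0.51. The top of the range needs every feature at the 20% ceiling.
- **The shrinkage can be modest.** It lessens where other variables predict the missing values. Even at 20% missing, nominal power at 100 per group stays at 80.7% (78% by simulation), close to the planned 80%.

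**Conclusion.** The point holds in conditional form. The order set out in section 7.1 most naturally gives one imputation for both uses. If it contains the classifier's label, the cross-validated AUC for pure noise is about 0.51-0.56 at 5% missing, 0.55-0.59 at 10% and 0.60-0.75 with every feature at the 20% ceiling. If it omits group, a 0.50 SD difference becomes about 0.48, 0.45 and 0.40.

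These figures rest on assumed missing rates and feature counts, values missing completely at random, independent features, no informative auxiliary variables for the shrinkage, and a classifier label that is also in the imputation model for the leak. The effect is minor with little missingness and few features, and material near the ceiling with large omics or imaging panels. The change should be made before analysis. It is not evidence that any planned result is already invalid.

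**What to change.** Replace the single imputation instruction in section 7.1 with one rule per use:

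- **Group comparisons, correlations and regressions:** multiple imputation with group, covariates and outcome in the imputation model.
- **Random Forest/ROC:** start from the unimputed data. Fill gaps inside each training fold without the classifier's label (for example the training-fold median or nearest neighbours), and apply the same fitted fill to the held-out subjects. Worded in terms of the classifier's label, the rule works whichever label is chosen.
- **sCCA and PCA:** a fill that does not use the group label.

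In the simulations, the label-free fill inside folds returned the null AUC to 0.49-0.51, and imputation with group included returned the difference to 0.49-0.50.

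The cost is a few sentences and some analysis code, with no new data. The downsides are two imputation streams to maintain and a possibly lower reported AUC.
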